In a phase I study, carried out in 30 healthy subjects, PRO-157 was applied 4 times a day (every 6 hours), for 10 days. There were 3 follow-up visits on days 2, 4 and 7, and a final visit on day 11. The primary safety variables were: visual acuity, ocular surface staining with fluorescein and lysamine green, PIO and presence of EA. The tolerability variables were burning, hyperemia, chemosis, foreign body sensation, lacrimation, pruritus and secretion. In the safety variables there were no changes between the baseline and the final visit, there were no adverse events. Regarding tolerability, burning was the most common symptom in all visits, reporting as mild in 48-70% of cases, the highest incidence of burning reported as severe was on day 2, with 27% of cases. [34]

5.3.1.5 Clinical efficacy studies.

Studies have been reported in systemic application, nevertheless we will only show those of ophthalmic route, for more information on efficacy clinical studies by other routes of administration, refer to the manual of the researcher of PRO-157.

In a phase II, multicentric, double masked, randomized and active control study, the efficacy, in the treatment of bacterial conjunctivitis, of the PRO-157 formulation (pazufloxacin 0.6%) was tested in 3 different posologies (twice per day, three times a day and 4 times a day), compared to the ophthalmic solutions of moxifloxacin 0.6% (Vigamoxi®, Alcon Laboratories) and gatifloxacin 0.3% (Zymar, Allergan Inc.) 3 times a day. A total of 300 eyes with a clinical diagnosis of bacterial conjunctivitis were included in the study. The intervention lasted 7 days. The efficacy variables were the clinical remission of the disease and bacterial eradication on day 7. The instillation of 1 drop 3 times a day of PRO-157 for 7 days, is the dose that showed greater efficacy in relation to the

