- III. History Users of contact lenses who are not willing to suspend their use during the study.
- IV. Users of any formulation with ophthalmic application, including lubricants, that can not, or do not want to suspend it during the study.
- V. Antecedents of eye surgery 6 weeks prior to study entry.
- VI. Viral or allergic conjunctivitis.
- VII. Active uveitis.
- VIII. Active ulcerative keratitis.
- IX. Recurrent corneal erosion syndrome
- X. Antecedent of hypersensitivity or allergy to fluoroquinolones.

6.2.3 Elimination criteria.

- I. Subject's decision. The subject may decide unilaterally to withdraw from the study at any time.
- II. Pregnancy.
- III. Presence of a serious adverse event (EAS), including the presence of hypersensitivity.
- IV. Investigator's decision:
 - a. Due to the presence of an EA that, although not serious, at the discretion of the IP merits the prescription of a medicine not authorized in the protocol.

V. Any deviation to the protocol that affects the security of the subject.

6.2.4 Identification of the subject.

The patients of the study will be identified by a number and the initials of their name.

The initials of the study subject will be obtained by starting with the first letter of the name, followed by the first letter of the first surname and the first of the second, obtaining maximum three letters, in case the person has two names or a compound surname will always be used the first letter of the first name or last name composed.

Example:

1. Adolfo Daniel Mercado Carrizales

a. a. Initials: AMC

2. Juan De la Torre Orozco

a. Initials: JDO

[figure not shown]
3. Luis Carlos Pérez-Gómez Ramírez

a. Initials LPR

In the counting stage, the participant number will be assigned consecutively, using 3 consecutive digits. Once the subject has been selected, he will be assigned a number with which he will be identified throughout the study. Said code will be composed of eight numbers in the following order from left to right:

- Three digits of the molecule under study according to the denomination by the sponsor.
- Two digits corresponding to the research center number
- Three digits of the number consecutive to its inclusion assigned in the research center.

Example:

6.3 Intervention.

6.3.1 Managed treatments.

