- By means of the revision of the daily tool of the subject.

Procedure to monitor adherence:

- The evaluation of the adherence by means of the diary of the subject will be carried out in the following way:

$$Ad = (A_r)100/A_i$$

Where:

Ad = Adherence

Ar = registered applications.

Ai = Indicated applications.

Only subjects with a minimum adherence of 80% by means of the subject's daily tool will be considered for efficacy analysis.

6.3.3 Treatments and concomitant interventions allowed and prohibited before and during the study.

The subjects admitted correctly to the study, who meet the eligibility criteria, may continue with the systemic treatment of the underlying diseases. If during the development of the study they require the implementation of a new permitted medication, they may do so. All concomitant medications used must be duly reported in the notes of the clinical file and in the corresponding section.

Allowed medications:

- Ophthalmic:

All permitted medications applied via ophthalmic during the study, must wait a minimum period of 10 minutes from the last application of the treatments under study or reference. The above in order to avoid the interaction of treatments in the tear film, based on the tear flow index and the physiological tear volume. [36]

- o Tetracaine 0.5%
- o Tropicamide 0.8% / Phenylephrine 5%

- Administered by a route other than ophthalmic:

- o Medicines whose effect may be susceptible of modifying any of the parameters of efficacy, safety or tolerability of this research protocol must notify their clinical monitor or the scientific committee of the sponsor to judge the convenience of entry, continuation or elimination of the participant according to correspond

Any medication allowed that is used, besides appearing in the clinical note, must be registered in the section of concomitant medications in the CRF.

Prohibited drugs:

- Any medication with ophthalmic application that is not on the list of allowed medications. The rest period prior to entering the study is according to the table.

Table 4. Rest period of medications with ophthalmic application.

Type of medication	Example	Rest period
Ophthalmic anti-inflammatories (Steroids and NSAIDs)	Diclofenac	48 hours
	Dexamethasone	
Ophthalmic antibiotics	Ciprofloxacin	24 hours
	Tobramycin	
Any other ophthalmic medication, including lubricants	Hipromellose	2 hours
	Timolol	

6.3.4 Treatment management.

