For the reporting of adverse events all participating subjects who were randomly assigned to an intervention group will be considered. The results will be expressed in number of subjects.

The final report of the results will be shown in tables or graphs, as appropriate.

In case of loss of cases (data), they will not be replaced by any situation to complete the sample size.

According to the data obtained, the sponsor will decide to perform a subanalysis by age groups, which will have no influence on the final result.

8.3.2 Additional analyzes.

An internal analysis will be made to know the changes that occur between each visit. It is the sponsor's prerogative to request an additional analysis of the data, during the conduction of the study or at the end of this.

8.3.3 Population analysis and management of missing data.

The effectiveness analysis will consider those cases in which the measurements of the baseline and final visit are met. Those subjects who do not comply with any of these measurements will not be integrated into the final database to evaluate the effectiveness. Nevertheless, an intention to treat analysis (ITT) will be carried out.

The safety assessment will include in the analysis all those subjects (considering one eye or both) who have been exposed at least once to any of the interventions regardless of the visit in which they were eliminated from the study.

9. Methods Monitoring.

9.1 Data monitoring.

Monitoring visits by a site monitor from Sophia Laboratories, S.A. of C.V. are intended to confirm that the studies sponsored by Sophia Laboratories, S.A. of C.V. they are conducted in accordance with the ethical principles that have their origin in the Declaration of Helsinki and that are consistent with Good Clinical Practices and with the applicable regulatory requirements (verifying a continuous compliance with the protocol, amendment or amendments, reviewing accounting records of the product under investigation, verifying that the personnel of the site and the facilities remain adequate to carry out the study).

The researcher must ensure that they have sufficient time, space and qualified personnel for the monitoring visits.

In order to carry out the monitoring review, it is mandatory to provide direct access to all source data and those related to the study site. The monitor will conduct a review of the CRF and a

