Information about the type of adverse event, adverse reaction or suspected adverse reaction to the product under investigation or to the study medication, as appropriate. The date on which the adverse event occurs is reported, as well as in which the Investigator is aware of it, date of resolution or outcome, as applicable. The clinical diagnosis is indicated. If a lack of therapeutic response is detected to the investigational product and / or investigational medication, it should be reported as an adverse reaction. Include in concomitant medications the therapy used for the pharmacological management of the adverse event, suspected adverse reaction, adverse reaction. Record the outcome or resolution of the event: patient recovered without sequelae, with sequelae, not recovered. Patient who presented death due to adverse reaction / adverse event, patient who presented death and it is judged that the drug could have contributed, patient who presented death and this is not related to the investigational product or drug, or indicate that it was not known what the consequence of the event is.

Consign information about the product or drug under investigation or the drug associated with the adverse event, adverse reaction or suspected adverse reaction. As applicable, information concerning generic denomination, distinctive denomination or product code in research and / or investigational medication should be recorded, as appropriate according to the methodological design of the study, this is relevant in the case of blinded studies or those where they use placebo as comparators, since there are circumstances that justify opening the cecum to determine if the adverse event, the adverse reaction or suspected adverse reaction may be attributable to the active agent, the combination of active agents, or the substance (s). s) pharmacologically inert (s), such as vehicles or additives, as appropriate to the clinical research phase in which the development of the drug is located.

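### Efficacy is analysed in adherent completers, with no rule that scores failure-driven withdrawals as non-remission and an ITT analysis that is neither defined nor ranked; this can bias towards non-inferiority

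*Combined protocol and SAP*

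**What the plan says.** Section 8.3.3 defines the efficacy population: "The effectiveness analysis will consider those cases in which the measurements of the baseline and final visit are met". It continues: "Those subjects who do not comply with any of these measurements will not be integrated into the final database to evaluate the effectiveness". The next sentence adds: "Nevertheless, an intention to treat analysis (ITT) will be carried out". Nothing more is said about ITT: no population, no handling of a missing day-8 result, and no statement of which analysis decides.

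Section 6.3.2 adds a second filter: "Only subjects with a minimum adherence of 80" per cent, by diary, count for efficacy. Adherence is recorded applications divided by indicated applications. The denominator for someone who stops early is not stated.

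Three further rules bear on who leaves:

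- Section 6.2.3 eliminates for "Presence of a serious adverse event (EAS), including the presence of hypersensitivity". Under IV.a it also eliminates for a non-serious adverse event that "at the discretion of the IP merits the prescription of a medicine not authorized in the protocol".
- Section 9.3.1.1 begins a rule with "If a lack of therapeutic response is detected to the investigational product" and requires that such a case be reported as an adverse reaction.
- Section 6.3.3 permits only tetracaine and tropicamide/phenylephrine by the ophthalmic route, so any other ophthalmic antibiotic is unauthorised.

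The primary outcome is remission on day 8 (6.4.2.1). It is scored Yes only with grade 0 for both hyperemia and secretion, and No otherwise (6.4.3.1). Section 6.5 describes no efficacy assessment at early withdrawal.

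**The concern.** In a non-inferiority trial the analysis set must not lose failures, because doing so usually makes a worse arm look closer to the better one. Here a non-responder can leave the efficacy set by an indirect route. The lack of response is recorded as an adverse reaction. The investigator may judge that it merits an unauthorised medicine, and the participant is then eliminated. That participant is lost to efficacy if the final visit does not take place, or if adherence falls below 80%.

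The ITT analysis could protect against this, but as written it does not. Its treatment of missing outcomes could be chosen after the data are seen. If ITT and the completer analysis disagreed, the plan would not say which one governs. The primary conclusion is what is at stake.

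**Working it through.** **The plan's own figure.** From 6.6.1: p = 0.88, p0 = 0.94, margin 15 points, one-sided alpha 5%, power 90%. With the margin entered as -0.15, the printed formula gives

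0.88 × 0.12 × [(1.645 + 1.282) / (0.88 - 0.94 + 0.15)]² = 111.65, so 112.

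Allowing for 30% losses, 112 / 0.70 = 160, or 80 per arm. Both stated figures reproduce. Whether that formula suits a two-arm trial is a separate question. The allowance is 160 - 112 = 48 participants, 24 per arm, leaving 56.

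**The adherence rule.** Three drops a day for 7 days is 21 applications, and 0.80 × 21 = 16.8, so 17 are needed.

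- Stopping at the end of day 5: at most 15/21 = 71%, excluded even if seen on day 8.
- Stopping at the end of day 6: up to 18/21 = 86%, retained.
- If only doses due up to withdrawal counted, the day-5 participant could reach 15/15 = 100%.

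The text does not say which denominator applies.

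**Effect of losing failures.** Suppose a share f of true failures drops out of an arm whose true remission rate is p.

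- Apparent rate: p / [p + (1 - p)(1 - f)].
- Number left: 80 × [p + (1 - p)(1 - f)].
- Chance of declaring non-inferiority: Φ[(difference + 0.15)/SE - z], with unpooled SE.

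Section 8.3.1 names only tests of difference, so comparing a lower confidence limit with the 15-point margin is my assumption. The true rates are set at the margin: gatifloxacin 0.94, PRO-157 0.79. Every f is assumed.

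Worked case, f = 0.25 in both arms: 0.94/0.985 = 0.954 and 0.79/0.9475 = 0.834, a difference of -12.1 points with 78.8 and 75.8 left. SE = 0.0488, and Φ(0.0295/0.0488 - 1.645) = 14.9%.

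| Failures lost: gatifloxacin / PRO-157 | Apparent difference (points) | False non-inferiority, one-sided 0.05 | One-sided 0.025 |
|---|---|---|---|
| 0 / 0 | -15.0 | 5.0% | 2.5% |
| 25% / 25% | -12.1 | 14.9% | 8.7% |
| 50% / 50% | -8.6 | 43.7% | 31.8% |
| 75% / 75% | -4.7 | 93.5% | 88.5% |
| 0 / 50% | -5.7 | 63.8% | 51.5% |
| 50% / 25% | -13.5 | 9.1% | 5.0% |
| 50% / 0 | -17.9 | 1.3% | 0.5% |

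Simulation (400,000 runs, one-sided 0.05) for the four equal-loss rows gives 6.1%, 17.3%, 46.3% and 89.4%, in reasonable agreement.

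Equal shares still bias the result because the worse arm has more failures to lose: 0.21 × 80 = 16.8 against 0.06 × 80 = 4.8. Few participants are involved. At 25% the loss is 4.2 + 1.2 = 5.4 of 160 (3.4%); at 50% it is 8.4 + 2.4 = 10.8 (6.8%).

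**Two contrasts.**

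- If 30% are lost regardless of outcome (56 per arm), the rates stay at 0.94 and 0.79 and the false rate stays at 5%.
- If those same losses were all scored as failures, the rates become 0.7 × 0.94 = 0.658 and 0.7 × 0.79 = 0.553. The difference shrinks to -10.5 points and the false rate rises to 14.5% (8.5% at 0.025). Blanket failure scoring is therefore not a safe default.

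**The case against.** The strongest reply is that an ITT analysis is planned, introduced by a word that marks it as an exception to the exclusion. That stands as a partial safeguard. It does not settle the matter, because the analysis has no outcome rule and no rank.

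A reader might go further than the text allows in four ways:

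- *Non-response is itself grounds for elimination.* It is not listed in 6.2.3. The route runs through 9.3.1.1 and criterion IV.a and depends on the investigator's judgement.
- *Every day-5 failure disappears.* Section 8.3.3 excludes on missing measurements, not on elimination as such. A non-responder who continues with adequate adherence and attends on day 8 is scored No. Under 8.1.1, sites must also call non-attenders and try to rebook them.
- *Burning will drive more PRO-157 participants out.* In phase I (5.3.1.4), "the highest incidence of burning reported as severe was on day 2, with 27% of cases". Those were 30 healthy subjects dosed four times a day for 10 days, with no comparator described. The randomised phase II study, which included gatifloxacin, found no between-group difference in tolerability symptoms, burning among them (5.3.1.5). The documents do not show that PRO-157 would have more dropout.
- *The 30% allowance sizes the bias.* Section 6.6.1 attributes it to probable losses and balance between groups, not to failures.

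An adherence-based set is also ordinary in non-inferiority trials. The fault is its use as the efficacy set without a failure rule or a ranked ITT analysis beside it.

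**Conclusion.** The concern holds as a conditional one. Following the stated rules can remove failures from the efficacy comparison, and nothing prevents a non-inferiority claim from resting on that set alone.

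The size depends on assumed loss patterns. With true rates at the margin and 80 randomised per arm, losing 25% to 50% of failures equally raises the false non-inferiority rate from 5% to about 15% to 44% (one-sided 0.05), or from 2.5% to about 9% to 32% (one-sided 0.025). The bias is absent when losses are unrelated to outcome and reverses when mainly gatifloxacin failures are lost. An unconditional statement that the plan favours PRO-157 is not supported. The need for a rule is, because the conclusion can change and the plan does not say what would then decide.

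**What to change.** Before unblinding, amend the analysis text:

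1. In 8.3.3, define the ITT set as all randomised participants. Score day-8 remission No for anyone withdrawn for lack of response or an adverse event, or who received an unauthorised ophthalmic anti-infective or anti-inflammatory before day 8.
2. State a rule for other missing day-8 values, with a sensitivity analysis. Multiple imputation with a tipping-point check is one acceptable choice. Do not simply score all missing values as failures.
3. Keep the adherent completer set as the per-protocol analysis. Retain failure-driven withdrawals in it as failures, and compute adherence on doses due up to withdrawal.
4. Require both sets to support non-inferiority before it is claimed.
5. Reword 6.3.2 so that the 80% rule defines only the per-protocol set.
6. Record the reason for every elimination. Section 8.1.1 asks for it only from non-attenders who cannot be rescheduled.

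The cost is a little more analysis, slightly lower reported remission rates, one more recorded item, and an amendment that needs committee review and regulatory authorisation under 10.2.

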
Reference product, dose and route of administration, batch:
 
 1. Zymar®. Gatifloxacin 0.3%. Prepared by Allergan, S.A. of C.V. 
 - Dosage: 1 drop, 3 times a day during the waking period in both eyes (at approximate intervals of 6 hours), for 7 days. - Route of administration: topical ophthalmic

Evaluation criteria:
 
Effectiveness:
 
 • Primary 
 ◦ Clinical remission of acute bacterial conjunctivitis on day 8, absence of: 
 - Conjunctival secretion - Bulbar conjunctival hyperemia • Secondary 
 ◦ Bacterial eradication, on day 8, in the cultures of patients with positive basal cultures. ◦ Degree of conjunctival hyperemia during visits ◦ Degree of conjunctival secretion during visits ◦ Overall researcher's rating of clinical changes and symptoms during visits 
Security:
 
 • Adverse events (EA)

Statistical methodology:
 
The result of the continuous quantitative variables will be presented in measures of central tendency.
 
The normal distribution of the results will be obtained through the Kolmogorov-Smirnov and Shapiro-Wilks test. The statistical analysis of the continuous quantitative variables to find significant differences (p) will be in the analysis between groups: t test for independent groups.

2. Content.

1. SUMMARY	3
2. CONTENT	5
3. ABBREVIATION INDEX	9
4. ADMINISTRATIVE STRUCTURE OF THE STUDY	11
5. INTRODUCTION	13
5.1 THEORETICAL FRAMEWORK	13
5.1.1 THEORETICAL FRAMEWORK	13
5.1.2 CLINICAL PICTURE OF ACUTE BACTERIAL CONJUNCTIVITIS	14
5.1.3 TREATMENT OF ACUTE BACTERIAL CONJUNCTIVITIS	14
5.2 DEFINITION OF THE PROBLEM AND FUNDAMENTAL REASON	15
5.3 BACKGROUND	16
5.3.1 PAZUFLOXACIN	16
5.3.1.1 Pharmacodynamics	16
5.3.1.2 Eyeball pharmacokinetics	16
5.3.1.3 Preclinical studies	16
5.3.1.4 Clinical safety studies	19
5.3.1.5 Clinical efficacy studies	19
5.3.1.6. Safety and tolerability	20
5.4 JUSTIFICATION	20
5.5 OBJECTIVES AND HYPOTHESIS	20
5.5.1 GENERAL PURPOSE	20
5.5.2 SPECIFIC OBJECTIVES	21
5.5.3 SECONDARY OBJECTIVES	21
5.5.4 HYPOTHESIS	21
5.6 DESIGN AND STUDY PLAN	21
5.6.1 DISCUSSION OF THE STUDY DESIGN	22
6. MATERIAL AND METHODS. PARTICIPANTS, INTERVENTIONS AND VARIABLES	22
6.1 STUDY CENTER	22
6.1.1 ORGANIZATION OF THE CENTER	23
6.1.2 DOCUMENTATION TO BE DELIVERED TO THE SPONSOR	23

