- To evaluate the efficacy of PRO-157 by decreasing the degree of hyperemia and conjunctival secretion during visits.
- To evaluate the efficacy of the ophthalmic solution of gatifloxacin 0.3%, by means of the clinical remission of acute bacterial conjunctivitis on day 8, by means of the absence of conjunctival secretion and bulbar hyperemia.
- To evaluate the efficacy of the ophthalmic solution of gatifloxacin 0.3%, by decreasing the degree of hyperemia and conjunctival secretion during visits.

5.5.3 Secondary objectives.

- To evaluate the efficacy of PRO-157 by bacterial eradication with respect to baseline, on day 8.
- To assess the efficacy of PRO-157 by decreasing the researcher's overall rating of clinical changes and symptoms during visits.
- Evaluate the safety of PRO-157 through the presence of EA.
- To evaluate the efficacy of the ophthalmic solution of gatifloxacin 0.3%, by bacterial eradication with respect to the baseline on day 8.
- To evaluate the efficacy of the 0.3% gatifloxacin ophthalmic solution, by decreasing the researcher's overall rating of clinical changes and symptoms during visits.
- To evaluate the safety of the ophthalmic solution of gatifloxacin 0.3%, through the presence of EA.

5.5.4 Hypothesis.

H0I: The ophthalmic solution PRO-157 is not inferior in the treatment of bacterial conjunctivitis, compared to the ophthalmic solution of gatifloxacin 0.3%, by means of the clinical remission of the disease.

Ha: The ophthalmic solution PRO-157 is inferior in the treatment of bacterial conjunctivitis, compared to the ophthalmic solution of gatifloxacin 0.3%, by means of the clinical remission of the disease.

5.6 Design and plan of the study.

Phase III clinical study of noninferiority, multicenter, double blind, with comparative group, of parallel groups, with randomization. Patients with clinical diagnosis of acute bacterial conjunctivitis will participate, who will be randomly assigned to 2 intervention groups. One group will receive the study formulation PRO-157 and the other group will be exposed to gatifloxacin 0.3%.

[figure not shown]

Figure 4. Study design.

5.6.1 Discussion of the study design.

In clinical research it is common to propose trials with the objective of evaluating the efficacy of a product under investigation against a reference medicine or active control, in order to compare the new product under investigation from a clinical or statistical point of view to a drug commercially available

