The refund will be made by the research center when the sponsor indicates it. Prior to the return the research center must make a count of the assigned medication and the remaining medication, with the aim of creating an inventory which serves for the final filling of the medication return form.

6.4 Outcome variables.

6.4.1 Security variables.

- Adverse events

6.4.2 Efficacy variables.

6.4.2.1 Primary outcome variables.

- Clinical remission of acute bacterial conjunctivitis on day 8, defined by the absence of:
 - Conjunctival secretion
 - Bulbar conjunctival hyperemia.

6.4.2.2 Secondary outcome variables.

- Bacterial eradication, on day 8, in the cultures of patients with positive basal cultures. Bacterial eradication will be defined as the absence of bacterial species that were present in the culture of the baseline visit.
- Degree of conjunctival hyperemia during visits
- Degree of conjunctival secretion during visits
- Overall investigator rating of clinical changes and symptoms during visits.

6.4.3 Methods and scales to be used for the measurement of the variables.

The variables and their units of measurement are included in **Table 5 Method of measuring variables**.

Variable	Unity	Symbol	Type	Method of measurement
Overall rating	Degrees	---	C. Ordinal	Direct observation and interrogation
Bacterial eradication	Colony forming units	UFC	C. Continuous	Secretion culture
Adverse events	Number of cases	N	C. Discrete	Count
Conjunctival bulbar hyperemia	Degrees	---	C. Ordinal	Direct observation (Biomicroscopy)
Clinical referral	If not	---	Qualitative rated	Direct observation (Biomicroscopy)

Variable	Unity	Symbol	Type	Method of measurement
Conjunctival secretion	Degrees	---	C. Ordinal	Direct observation (Biomicroscopy)

Table 5 Method of measuring variables.

The following describes the methods and scales that will be used for the measurement of the variables, which are in strict alphabetical order of the procedure:

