6.5.2.4 Final Visit

- Pregnancy test: see 6.5.2.1 Baseline visit.
- Conjunctival secretion sampling: see section 6.4.3.4 Conjunctival secretion sampling for bacterial culture
- Ophthalmological examination: see 6.5.2.1 Baseline visit.
- Biomicroscopy: see 6.4.3.1 Biomicroscopy
- Global qualification of the researcher: see 6.4.3.2 Global qualification of the researcher
- Evaluation of concomitant medications: see 6.5.2.1 Baseline visit.
- Assessment of adverse events: see 6.4.3.3 Evaluation of adverse events
- Continuity evaluation: see 6.5.2.2 Visit 1
- Adherence evaluation: see 6.5.2.2 Visit 1
- Global qualification of the researcher: see 6.4.3.2 Global qualification of the researcher
- Return of the medication: refers to the delivery, by the subject, of the excess medication to the research center.
- Return of the subject's diary: refers to the delivery, by the subject, of the tool "subject's diary" to the research center.

6.5.2.5 Security call:

- Assessment of adverse events: see 6.4.3.3 Evaluation of adverse events.

6.5.3 Diagram of the study.

[figure not shown]

Figure 6. Diagram of the study.

6.6 Sample size.

The sample size calculated for the present study is 160 eyes. They plan to recruit 160 subjects, each one will provide an eye for the study, for the analysis of efficacy.

Divided into two intervention groups, each group will be comprised of 80 eyes.

6.6.1 Calculation of the sample size.

The sample size was calculated using the formula for variables of two proportions, likewise the data was entered into the online calculator, software developed in: www.powerandsamplesize.com based on Chow S et al. [39]

Based on the final report of the Phase II clinical study, and the difference found between the intervention of PRO-157, three times a day, against gatifloxacin 0.3%, the calculation of the sample size was made.

The dosage that showed the greatest efficacy was the instillation of 1 drop three times a day. A cure percentage of 88% was observed with the mentioned group. The group that received Gatifloxacin reported a cure rate of 94%. Nevertheless, there was no statistical difference between the groups. [35]

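### Lack of therapeutic response is recorded as an adverse reaction and not tabulated apart, so some efficacy failures also enter the only safety count

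*Combined protocol and SAP*

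**What the plan says.** The rule is in protocol section 9.3.1.1, on recording adverse events in the case report form: if "a lack of therapeutic response is detected to the investigational product and / or investigational medication, it should be reported as an adverse reaction". It names no arm, does not define lack of response and gives no visit at which it is judged.

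Adverse events are the only safety variable (synopsis and section 6.4.1). The secondary objectives in 5.5.3 rest on them, for example "Evaluate the safety of PRO-157 through the presence of EA", with a matching objective for gatifloxacin. Section 5.6.1 adds the aim of comparing the two safety profiles.

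Table 5 in 6.4.3 gives the unit as "Number of cases". Section 8.3.1 says "For the reporting of adverse events all participating subjects who were randomly assigned to an intervention group will be considered", and then "The results will be expressed in number of subjects". Neither place sets lack-of-response entries apart.

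Non-response is already captured as efficacy in two ways. Under 6.4.3.1, remission is a yes only with grade 0 for both hyperemia and secretion. Under 6.4.3.2, the investigator's global rating separates cured (0), improved (1), unchanged (2) and worse (3).

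**The concern.** A participant whose conjunctivitis does not respond, and who has no harm from the drops, is an efficacy failure. Under 9.3.1.1 the same participant can also become a safety case, labelled a reaction before the causality assessment in 9.3.1.4 has been made. The safety table then partly repeats the efficacy result, and an arm with more non-responders shows more events without any toxicity.

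The overlap is awkward in this trial. Bulbar hyperemia is a component of the primary endpoint, and section 5.3.1.6 lists conjunctival hyperemia among the symptoms reported with PRO-157. A single undivided count cannot tell persisting disease from irritation by the drug. Under 9.3.1.3, the safety profile from non-serious events goes to the regulator in the final report.

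**Working it through.** **Inputs from the plan.** Section 6.6.1 takes the PRO-157 rate from phase II ("A cure percentage of 88% was observed with the mentioned group") and uses 94% for gatifloxacin, so the failure proportions f are 0.12 and 0.06. Section 6.6 gives 80 eyes, one per participant, in each arm.

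The plan has no figure for this point. Its one calculation confirms that these are the rates it used: 0.88 × 0.12 × 8.564 / (0.88 − 0.94 + 0.15)² = 0.1056 × 8.564 / 0.0081 = 111.6, so 112; and 112 / 0.70 = 160. Here 8.564 is the squared sum of the normal quantiles for one-sided 5% and 90% power. Whether that formula suits a two-arm comparison is a separate matter.

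**Assumptions.** The planning cure rate stands for day 8 remission. The background proportion b with any other adverse event is the same in both arms and independent of failure; the documents give no value, so 0 to 30% is shown. The share s of failures entered as lack of response is also not given, so 0.25 to 1 is shown.

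**Formula.** Proportion with at least one counted event = 1 − (1 − b)(1 − s × f).

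**Ceiling** (s = 1, b = 0): 80 × 0.12 = 9.6 v 80 × 0.06 = 4.8 participants, or 12% v 6%.

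**Worked case** (b = 0.10):
- s = 1: 1 − 0.90 × 0.88 = 0.208 v 1 − 0.90 × 0.94 = 0.154
- s = 0.5: 1 − 0.90 × 0.94 = 0.154 v 1 − 0.90 × 0.97 = 0.127
- s = 0.25: 1 − 0.90 × 0.97 = 0.127 v 1 − 0.90 × 0.985 = 0.1135

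| Background b | Share entered s | PRO-157 | Gatifloxacin | Ratio |
|---|---|---|---|---|
| 0 | 1 | 12.0% | 6.0% | 2.0 |
| 10% | 1 | 20.8% | 15.4% | 1.35 |
| 10% | 0.5 | 15.4% | 12.7% | 1.21 |
| 10% | 0.25 | 12.7% | 11.4% | 1.12 |
| 30% | 1 | 38.4% | 34.2% | 1.12 |
| 30% | 0.25 | 32.1% | 31.1% | 1.03 |

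Over b from 0 to 30%, the artificial difference is 6.0 to 4.2 percentage points with s = 1 and 1.5 to 1.05 points with s = 0.25. With s = 0 the arms are equal at any background rate.

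**Equal efficacy.** If both arms cured 88%, s = 1 and b = 10% would give 20.8% in each. Both are inflated above the 10% background, but neither looks worse than the other.

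**Formal test.** At the planning rates and 80 per arm, a two-sided 5% test would flag the artefact in about 26% of trials at the ceiling, and in about 14% with b = 10% and s = 1.

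**The case against.** Several counter-arguments have force.

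- **Not every primary failure is a lack of response.** A reader might infer that all failures of the primary endpoint are counted again. The documents do not say so. A participant left with grade 1 hyperemia fails remission but may be rated improved, and nothing then requires an adverse-reaction entry. This stands, and it makes 9.6 v 4.8 a ceiling.
- **A doubling is not the expected result.** A ratio of 2.0 needs no other adverse events at all, while 5.3.1.6 reports burning, hyperemia and foreign body sensation with PRO-157. This stands; the table shows how fast the ratio falls.
- **The tilt needs a true efficacy difference.** Section 6.6.1 says that the phase II rates did not differ statistically. This stands, so the documents do not show that PRO-157 will look less safe.
- **The entries could be identified later.** Section 9.3.1.1 asks for event type and diagnosis, and 9.3.1.3 for seriousness, intensity and relationship. This stands in part: a reader of listings could find them, but no separation is planned, so it would be decided after the data are in.
- **Pharmacovigilance rules may require the report.** Section 9.3.1 refers to outside regulations that cannot be judged from these documents. That does not defeat the point, because a report can be kept and still be tabulated apart.

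**Conclusion.** The point holds as a gap in definition and tabulation. Following the plan as written puts some efficacy failures into the only safety count, and any resulting tilt goes against the arm that is truly less effective. On the planning rates the ceiling is 6 percentage points. With other events at an assumed 10%, the ratio lies between 1.12 and 1.35 for a quarter to all of the failures entered; at 30% it lies between 1.03 and 1.12. A larger true deficit in efficacy would give a larger artefact.

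A reader might go further and conclude that the safety comparison no longer measures harm. The documents do not support that: genuine events are still recorded, and the effect is mainly a descriptive distortion. The primary non-inferiority conclusion is untouched, and the safety trigger based on event frequency in 9.2 counts only serious events. The sizes rest on the assumed background rate, the assumed share entered, and the phase II cure rates standing for remission. The change should be made, but the trial's main result does not depend on it.

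**What to change.** - **Section 9.3.1.1:** tie lack of therapeutic response to a rating already collected (for example, global rating 2, unchanged), state the visit at which it is judged, and flag such entries as lack of efficacy on the adverse-event page of the case report form. Keep any pharmacovigilance report that is required.
- **Section 8.3.1:** tabulate flagged entries on their own line, and give adverse-event and adverse-reaction incidence by arm both with and without them.
- **Keep in the adverse-event count:** worsening (rating 3) and any new or distinct untoward sign. Excluding worsening could hide real harm, because hyperemia is both a disease sign and a reported effect of PRO-157.

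The cost is a short addition to each of the two sections, one more coding category and one more table line. No data are lost and no clinical procedure changes.
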